### 5.1.2 AE date imputation

Date imputation is the creation of a new, complete date from a partial one according to an agreed and acceptable algorithm. Missing date for AE will be handled according to rules specified below. A partial date is simply an incomplete date e.g., DDOCT2001: the days are missing from this DDMMMYYYY date.

Partial AE start dates, if left partial, would ultimately mean the following:

It would not be possible to place the AE in time. Therefore, the treatment/dosage at the time of the event would be unknown. So, the event could not be reported/summarized appropriately – if at all.

Therefore, it is important to perform date imputation to ensure that as many data events are represented as correctly as possible. Of course, partial and/or missing dates should also be caught as edit checks and passed back to the investigator for resolution.

There **will be no** attempt to impute the following:

- **Missing** AE start dates
- AE start dates **missing the year**
- Partial/missing AE **end dates**

Table 5-2 AE/Treatment date abbreviations

	Day	Month	Year
Partial AE start date	<not used>	AEM	AEY
Treatment start date (TRTSTD)	<not used>	TRTM	TRTY

The following matrix Table 5-3 describes the possible combinations and their associated imputations. In the light grey boxes the upper text indicates the imputation and the lower text the relationship of the AE start date to the treatment start date (TRTSTD).

Study Code: CLCI699C2X01B

Table 5-3 AE partial date imputation algorithm

	AEM Missing	AEM < TRTM	AEM = TRTM	AEM > TRTM
AEY Missing	NC	NC	NC	NC
AEY < TRTY	Before TRTSTD (D)	Before TRTSTD (C)	Before TRTSTD (C)	Before TRTSTD (C)
AEY = TRTY	Uncertain (B)	Before TRTSTD (C)	Uncertain (B)	After TRTSTD (A)
AEY > TRTY	After TRTSTD (E)	After TRTSTD (A)	After TRTSTD (A)	After TRTSTD (A)

Table 5-4 AE/treatment date relationship and imputation legend

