- Dose Reduced/increased
- Drug interrupted/withdrawn

6. its outcome i.e., its recovery status or whether it was fatal

If the event worsens the event should be reported a second time in the CRF noting the start date when the event worsens in toxicity. For grade 3 and 4 adverse events only, if improvement to a lower grade is determined a new entry for this event should be reported in the CRF noting the start date when the event improved from having been Grade 3 or Grade 4.

Conditions that were already present at the time of informed consent should be recorded in medical history of the subject.

Adverse events (including lab abnormalities that constitute AEs) should be described using a diagnosis whenever possible, rather than individual underlying signs and symptoms.

Adverse event monitoring should be continued for at least 30 days following the last dose of study treatment.

Information about adverse drug reactions for the investigational drug can be found in the Investigator Brochure (IB).

Abnormal laboratory values or test results constitute adverse events only if they fulfill at least one of the following criteria:

- they induce clinical signs or symptoms

- they are considered clinically significant
- they require therapy

Clinically significant abnormal laboratory values or test results must be identified through a review of values outside of normal ranges/clinically notable ranges, significant changes from baseline or the previous visit, or values which are considered to be non-typical in subjects with the underlying disease.

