### 7.1.1 Primary endpoint

The assessment of safety will be based mainly on the frequency and severity of AEs, AESI and SAEs. See also Section 7.5.

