### 7.1.2 Statistical hypothesis, model, and method of analysis

The primary endpoint will be summarized descriptively, overall no formal analysis will be performed. No hypothesis will be tested.

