### 7.4.1 Adverse events (AEs)

Treatment emergent AEs are defined as those that started on or after the study medication, or those that started before study medication but worsened afterwards. AEs starting after 30 days after last dose of Osilodrostat treatment are not considered treatment emergent AEs.

Summary tables for adverse events (AEs) have to include only AEs that started or worsened during the on-treatment period, the treatment-emergent AEs. However, all safety data (including those from the post-treatment periods) will be listed and those collected during the post-treatment period are to be flagged.

The incidence of treatment-emergent adverse events (new or worsening from baseline) will be summarized by system organ class and/or preferred term, severity based on CTCAE grades (version 4.03 or higher), type of adverse event, relation to study treatment. The summary will include AEs regardless of study-drug relationship. The same analysis will be repeated for SAEs.

All treatment emergent AEs and SAEs will be listed. In this listing, the information on the relationship to study treatment will be included.

---

Study Code: CLCI699C2X01B

Adverse events will be coded using the Medical dictionary for regulatory activities (MedDRA) terminology using the latest available MedDRA version at the time of the analyses and the information of MedDRA version will be specified in the footnote of relevant outputs.

The following selection of AEs will be listed and summarized separately using Safety Set. AEs will be summarized for all grades and for grade 3 or 4 side-by-side.

- AEs
- SAEs
- AEs leading to study drug discontinuation
- AEs requiring dose adjustment or interruption
- AEs requiring additional therapy
- Adverse events of special interest (AESI)

For the legal requirements of ClinicalTrials.gov and EudraCT, two required tables on treatment-emergent adverse events which are not serious adverse events with an incidence greater than 2% and on treatment-emergent serious adverse events and SAE suspected to be related to study treatment will be provided by system organ class and preferred term on the Safety Set population.

If for a same patient, several consecutive AEs (irrespective of study treatment causality, seriousness and severity) occurred with the same SOC and PT:

- A single occurrence will be counted if there is  $\leq 1$  day gap between the end date of the preceding AE and the start date of the consecutive AE

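### AEs with no start year have no treatment-emergent default and, read literally, drop out of the primary safety tables; separately, partial start dates can be imputed after the AE's known end.

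*SAP*

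**What the plan says.** The primary endpoint is descriptive. SAP 7.1.1 states: "The assessment of safety will be based mainly on the frequency and severity of AEs, AESI and SAEs". SAP 7.1.2 adds: "No hypothesis will be tested".

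SAP 7.4.1 ties inclusion to the start date: "Treatment emergent AEs are defined as those that started on or after the study medication", or that began earlier and then worsened. Events starting more than 30 days after last dose are excluded. It continues: "Summary tables for adverse events (AEs) have to include only AEs that started or worsened during the on-treatment period".

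SAP 5.1.2 explains why partial start dates are imputed. If they were left partial, the AE could not be placed in time: "So, the event could not be reported/summarized appropriately". It then lists what will not be imputed: "Missing AE start dates", start dates lacking the year, and partial or missing end dates. Every cell in the missing-year row of Table 5-3 is NC (no convention), and the matching example in Table 5-5 is blank. The section asks for incomplete dates to be caught by edit checks and queried, and for them to appear as recorded in the listings.

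Other partial start dates are imputed from the AE month and year and the treatment start date alone. Rule B gives treatment start + 1 day, rule C the 15th of the month, rule D 1 July, rule A the first of the month and rule E 1 January.

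Protocol 10.1.1 counts AEs from written consent to this study and says: "Conditions that were already present at the time of informed consent should be recorded in medical history of the subject". Protocol 12.4.3, on missing values for the primary endpoint, is marked not applicable.

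**The concern.** An AE with no start year cannot be shown to have started on treatment. The worsening route does not help, because under Protocol 10.1.1 a worsening is a second entry with its own start date. Neither document says which class such an event takes, so the programmer must choose. The literal choice leaves it out of the AE, SAE and AESI summaries that form the primary endpoint.

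The SAP is also uneven here. Table 5-5 labels both the year-less date and `ddOCT2001` (treatment start 20OCT2001) as *Uncertain*. It places the second on treatment and leaves the first blank.

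A separate defect is that no rule compares the imputed start with a known AE end date. Some imputed starts are therefore impossible, and under rule B an event that ended before first dose can be tabulated as treatment-emergent. SAP 5.1.1 has a comparable check for last dose: it compares the imputed date with the start of study drug and corrects it.

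**Working it through.** **1. Reproduce the SAP's examples.** Coding Table 5-3 with the Table 5-4 legend and treatment start 20OCT2001 gives blank, 01JUL2000, 01JAN2002, 21OCT2001, 15SEP2001, 21OCT2001 and 01NOV2001. All seven match Table 5-5.

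**2. Dates with no year.** A wholly missing start, or one with a month but no year, returns no date. The test of SAP 7.4.1 (start on or after first dose) then has no input, so the event is unclassified.

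**3. Likely true class.** AEs count from roll-over consent, and earlier conditions go to medical history. Protocol 3.1 has no screening period and lets dosing start on enrolment. The window between consent and first dose should be short, so few undated AEs can precede dosing. Some could fall more than 30 days after last dose: Protocol 10.1.1 continues monitoring for at least 30 days, and Protocol 10.1.3 accepts later SAEs if a causal link is suspected.

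**4. Size of the undercount.** If the undated AE is the patient's only event of that term, incidence falls by 1/N. The protocol's only recent count is 100 enrolled at 8 April 2020 (Amendment 02 rationale); the final Safety Set is not given.
- Assumed N = 100: 1/100 = 1.0 percentage point.
- Assumed N = 150: 1/150 = 0.67 percentage points.

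The registry table in SAP 7.4.1 covers non-serious AEs above 2%. As a hypothetical case at N = 100, a term seen in 3 patients (3%) qualifies. With one of them undated it shows 2/100 = 2% and does not.

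**5. Imputed start against known end date** (treatment start 20OCT2001):

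| Recorded start | Known end | Rule | Imputed start | After end? | Treatment-emergent? |
|---|---|---|---|---|---|
| ddOCT2001 | 10OCT2001 | B | 21OCT2001 | yes | yes, wrongly |
| ddOCT2001 | 20OCT2001 | B | 21OCT2001 | yes | yes |
| ddmmm2001 | 15MAR2001 | B | 21OCT2001 | yes | yes, wrongly |
| ddSEP2001 | 05SEP2001 | C | 15SEP2001 | yes | no |
| ddmmm2000 | 01MAR2000 | D | 01JUL2000 | yes | no |
| ddNOV2001 | 01NOV2001 | A | 01NOV2001 | no | yes |
| ddmmm2002 | 01JAN2002 | E | 01JAN2002 | no | yes |

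**6. Which rules can fail.** Every calendar start day in 2000–2002 was enumerated for assumed 1-day AEs. The imputed start falls after the end as follows:
- Rule B, day missing: 20 of 31 start days. On 19 of these the AE ended before first dose and is called treatment-emergent.
- Rule B, day and month missing: 293 of 365, of which 292 are so misclassified.
- Rule C: 294 of 639, with no change of class.
- Rule D: 182 of 366, with no change of class.
- Rules A and E: none.

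For assumed 8-day AEs the counts are 13 of 31 and 286 of 365 (B), 147 of 639 (C) and 175 of 366 (D). These count calendar days and show where the rules fail. They are not expected frequencies, because few AEs in this study should precede first dose.

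**The case against.** The exclusion is implied, not written. A reader might infer that the SAP orders undated AEs out of every table; it does not, it is silent on their class. A reader might also take the SAP's warning about events that cannot be summarized as describing wholly missing dates. It is written about partial dates left partial, and carrying it over is inference, though a natural one.

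Controls exist. SAP 5.1.2 asks for edit checks and queries. Protocol 10.1.1 asks for AE start and end dates as far as possible. Protocol 11.2 requires queries on missing values, with necessary actions completed before lock. Protocol 11.3 requires full verification of SAE documentation and of data for the primary variables. Protocol 10.1.3 uses the SAE onset date to decide which study the SAE belongs to, so an SAE without even a year is unlikely to survive to lock. Undated AEs also remain in the listings.

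Finally, the two defects work in opposite directions, and the argument that few AEs precede first dose also makes the rule B error rare.

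All of this stands and limits the size of the problem. It does not close the gap. A query can still be open at a data cut-off: SAP 2.3.1 records three interim analyses and allows more. Nothing says what to do with a date that remains unresolved.

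**Conclusion.** The point holds as a gap in the rules with a small, unquantified effect. Read literally, an AE whose start year is unresolved at a cut-off or lock is left out of the treatment-emergent tables but kept in the listings. That omission can lower the primary endpoint and cannot raise it. The effect is 1/N per patient and term, about 1 percentage point on the assumption that N is about 100 and that the AE is the patient's only event of the term.

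The end-date defect is separate. Rules B, C and D can give an impossible start; only rule B alters the class, and it overcounts.

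A reader might infer a material downward bias, or a serious loss of SAEs. The documents do not support either. They give no count of undated AEs, the controls make undated SAEs especially unlikely, and the rule B error goes the other way. No hypothesis test is affected. The change is still worth making, because the rule is conventional and cheap and removes a discretionary choice from the primary endpoint.

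**What to change.** Amend SAP 5.1.2 and 7.4.1 before the next cut-off or lock:

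1. An AE whose start date is missing or lacks a year counts as treatment-emergent unless its known end date is before the first roll-over dose.
2. Where an imputed start is later than a complete known end date, set the start to that end date before assigning treatment-emergent status.
3. Listings keep the date as reported and flag every AE handled under 1 or 2.

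With treatment start 20OCT2001, `ddOCT2001` ending 10OCT2001 becomes 10OCT2001 and is no longer treatment-emergent. `ddOCT2001` ending 20OCT2001 becomes 20OCT2001 and remains so. `ddmmm2001` ending 15MAR2001 becomes 15MAR2001 and is no longer treatment-emergent.

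The cost is a few sentences and minor programming. Rule 1 may raise counts slightly, including a rare undated event that in truth began more than 30 days after last dose. Rule 2 may lower them slightly.

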**Relationship**

Before TRTSTD	Indicates AE start date prior to Treatment Start Date
After TRTSTD	Indicates AE start date after Treatment Start Date
Uncertain	Insufficient to determine the relationship of AE start date to Treatment Start Date

**Imputation Calculation**

NC/Blank	No convention/imputation
(A)	01MONYYYY
(B)	TRTSTD+1
(C)	15MONYYYY
(D)	01JULYYYY
(E)	01JANYYYY

The following Table 5-5 gives a few examples.

Table 5-5 AE imputation example scenarios

Partial AE start date	Treatment start date	Relationship	Imputation calculation	Imputed date
12mmYYYY	20OCT2001	Uncertain	NC	<blank>
ddmmm2000	20OCT2001	Before	(D)	01JUL2000
ddmmm2002	20OCT2001	After	(E)	01JAN2002
ddmmm2001	20OCT2001	Uncertain	(B)	21OCT2001
ddSEP2001	20OCT2001	Before	(C)	15SEP2001
ddOCT2001	20OCT2001	Uncertain	(B)	21OCT2001
ddNOV2001	20OCT2001	After	(A)	01NOV2001

Any AEs with partial/missing dates will be displayed as such in the data listings.

---

Study Code: CLCI699C2X01B

Any AEs which are continuing as per data cut-off will be shown as 'ongoing' rather than the end date provided.

## 5.2 DERIVATION RULES

### 5.2.1 AEs coding/grading

Adverse events are coded using the Medical dictionary for regulatory activities (MedDRA) terminology.

AEs will be assessed according to the Common Terminology Criteria for Adverse Events (CTCAE) version 4.03 or higher.

The CTCAE represents a comprehensive grading system for reporting the acute and late effects of cancer treatments. CTCAE grading is by definition a 5-point scale generally corresponding to mild, moderate, severe, life threatening, and death. This grading system inherently places a value on the importance of an event, although there is not necessarily proportionality among grades (a grade 2 is not necessarily twice as bad as a grade 1).

If CTCAE grading does not exist for an adverse event, the severity of mild, moderate, severe, and life-threatening, corresponding to Grades 1 - 4, will be used. CTCAE Grade 5 (death) will be summarized separately.

### 5.2.2 Study day

Definitions will be applied for all situations:

- Study day for post-treatment event = event date - first dose date + 1
- Study day for pre-treatment event = first dose date - event date

The first day of study drug is study day 1.

If duration is to be reported in weeks, duration in days will be divided by 7, likewise if in months, then duration in days will be divided by 30.4375 and if in years, duration in days will be divided by 365.25.

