#### 4.1.1 General definitions

*Baseline*

---

Study Code: CLCI699C2X01B

For this study the baseline visit (W1D1) corresponds to the End of Treatment visit in the relative parent study.

The data for all assessments (except Obtain informed consent, Confirmation of Clinical Benefit from Study Treatment, and End of phase disposition) will be taken from the parent study.

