#### *Date of first/last administration of study drug*

The start date of study drug is defined as the first date when a non-zero dose of study drug was administered in the roll-over study and recorded on the Dosage Administration Record (DAR) eCRF.

The date of last administration of study drug is defined as the last date when a non-zero dose of study drug was administered and recorded on DAR eCRF.

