## 5.3 DATA FROM PARENT STUDIES

Data referring to the disease history, as well as the height, were not collected in the study EDC but remained in the databases of the parent studies where the patients are coming from.

In addition, the data from the end of the treatment (or last visit) in the parent studies, will be extracted by the parent studies databases and transferred by the sponsor to the CRO. The date of the EOT visit from the parent study will be matched with the date of the baseline (W1D1) to guarantee the proper correspondence. The cases with a discrepancy exceeding one week between the two dates will be evaluated case by case.

For disease history they are the following ones:

- Time (months) to first study osilodrostat dose since diagnosis
- Classification at time of diagnosis
- Cushing's Disease Status
- Any previous surgery
- Any previous, non-LCI, treatments for Cushing's disease
- Any previous pituitary irradiation
- Baseline mean UFC.

---

Study Code: CLCI699C2X01B

---

For W1D1 visit the data to be transferred will regard the following topics:

- Vital signs (domain VS)
- ECG (domain EG)
- MRI (domains PR, FA)
- Laboratory (domain LB)

The data will be extracted as SAS datasets as close as possible to the domain structures reported in attachment 8.2.

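### SAP 5.2.2 gives dates before the first roll-over dose a positive study day, so they share day numbers with dates on treatment

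*SAP*

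**What the plan says.** SAP 5.2.2 (Study day) opens with "Definitions will be applied for all situations" and then gives two rules:

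- "Study day for post-treatment event = event date - first dose date + 1"
- "Study day for pre-treatment event = first dose date - event date"

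It fixes the origin with "The first day of study drug is study day 1". The section has no minus sign convention, separate label or flag for days before dosing.

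SAP 4.1.1 defines the start of study drug as the "first date when a non-zero dose of study drug was administered in the roll-over study". It uses the parent-study first dose only for total drug exposure. On baseline it says: "For this study the baseline visit (W1D1) corresponds to the End of Treatment visit in the relative parent study". SAP 5.3 has vital signs, ECG, MRI and laboratory data for that visit transferred from the parent-study databases.

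**The concern.** A study-day variable should show at once whether a record falls before or after the start of treatment. Under the rule for earlier dates it cannot: the value is positive and has the same name as the value from the other rule, so one number stands for two different dates.

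The design leaves room for such records. A baseline assessment from the parent study may be dated before the first roll-over dose. AEs count from roll-over consent (Protocol 10.1.1) and drug starts only after consent (Protocol 4.1), so an event can fall between the two. Any listing or derivation that uses study day would give these records an on-treatment number.

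The labels add a second ambiguity. Protocol 12.5.1.1 reserves the term post-treatment for the period from day 31 after last dose. If SAP 5.2.2 is read with that meaning, it has no formula for events during treatment.

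**Working it through.** **Inputs.** D is the first dose date and E the event date. The two formulas and the day 1 origin come from SAP 5.2.2. For a worked date I use the treatment start in SAP Table 5-5, D = 20OCT2001. That table contains made-up examples, so the dates show the arithmetic and say nothing about this trial's patients.

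**Step 1: reproduce the plan's own figure.** On the first-dose date, E − D + 1 = 0 + 1 = 1. This agrees with the stated day 1, so the rule for dates on or after first dose is sound.

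**Step 2: apply the rule for earlier dates as written, D − E.**

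| Date before dose | D − E | Date on or after dose with the same number | E − D + 1 |
|---|---|---|---|
| 19OCT2001 | 1 | 20OCT2001 (first dose) | 0 + 1 = 1 |
| 13OCT2001 | 7 | 26OCT2001 | 6 + 1 = 7 |
| 15SEP2001 | 35 | 23NOV2001 | 34 + 1 = 35 |

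**Step 3: general result.** If E is k days before D, the rule gives k. The date k − 1 days after D gets (k − 1) + 1 = k. Every pre-dose date therefore has a twin on or after first dose. The 365 dates before D take the numbers 1 to 365, exactly those of the 365 dates that start with D: 365 of 365 collide.

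**Step 4: reverse the sign.** With E − D for earlier dates, 19OCT2001 becomes −1, 13OCT2001 becomes −7 and 15SEP2001 becomes −35. The largest pre-dose value is −1 and the smallest value from first dose onward is 1. There is no day 0, and 0 of 365 collide.

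**Step 5: what depends on study day.** I compared the SAP's definitions with the formula.

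- Treatment emergence (SAP 7.4.1) rests on start relative to dosing: "Treatment emergent AEs are defined as those that started on or after the study medication". It ends 30 days after last dose.
- AE date imputation (SAP 5.1.2) compares month and year with the treatment start date.
- Exposure (SAP 7.3) uses first and last dose dates, date of death and data cut-off.
- Baseline (SAP 4.1.1) is a visit.
- Laboratory summaries (SAP 7.4.2) are bounded above by 30 days after last dose. The section restates no lower bound and does not mention study day.

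None of these selects records by study-day number.

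**The case against.** The strongest reply is that the slip has little effect, and most of that reply stands. The definitions in step 5 use dates or visits. Vital signs are listed by visit (SAP 7.4.3), and the transferred vital signs, ECG and laboratory records carry a baseline flag (SAP 8.2). No listing specification says that study day is displayed. SAP 8.2 does include study-day variables in the transferred datasets. It does not say which first dose they count from, so they do not show that the 5.2.2 formula was applied.

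A reader might also infer more than the documents support:

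- *Baseline values would enter the worst on-treatment summaries, or earlier events the treatment-emergent set.* This needs a program that selects by study day of 1 or more. The SAP specifies none, and for AEs such a program would contradict the written definition.
- *Discrepancies of weeks or years are to be expected.* AEs are collected from roll-over consent, conditions already present then go to medical history (Protocol 10.1.1), and earlier SAEs belong to the parent study (Protocol 10.1.3). Treatment can begin at enrollment (Protocol 3.1). Pre-dose AEs should therefore fall in the interval from consent to first dose.
- *Baselines up to a week before dosing are accepted.* SAP 5.3 says "The cases with a discrepancy exceeding one week between the two dates will be evaluated case by case", but the two dates are the parent end-of-treatment visit and W1D1. Neither is first dose, and no direction is given.
- *Issued interim listings are wrong.* SAP 2.3 lists the interim outputs without mentioning study day, and nothing shows that the formula was programmed literally.

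One could also read the rule as an unsigned count of days before dosing. That would work under its own label, but 5.2.2 calls both results study day and gives no such label.

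**Conclusion.** The rule is wrong as written, and this follows from the text alone: within one short section, the day before first dose and the day of first dose are both day 1. Every date before the first roll-over dose is affected; a record dated on the first-dose day is not.

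The demonstrated consequence is small. It is confined to listings or derivations that use study day, and the documents do not say which do or how many records precede first dose. They do not show that AE counts, exposure or any summary would change. This is a minor correction to a descriptive safety study, worth making because the rule must otherwise be either programmed literally, giving ambiguous days, or overridden silently, leaving program and SAP in disagreement.

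The conclusion assumes that first dose in 5.2.2 means the first roll-over dose, as SAP 4.1.1 defines it outside total exposure.

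**What to change.** In SAP 5.2.2:

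1. Before first dose: study day = E − D, which is negative, with no day 0.
2. On or after first dose: keep E − D + 1.
3. Name the rules *before first dose* and *on or after first dose*, so that post-treatment keeps its protocol meaning.
4. State that D is the first roll-over dose date.

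Then check whether any output from the interim analyses listed in SAP 2.3.1 used the formula, and correct only those that did.

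The cost is one line and two labels in the SAP, one derivation in the programs, and a short check of issued outputs. No new data are needed.
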